5.4. Examination of Covariates, Other Strata and Subgroups

5.4.1. Covariates and Other Strata

The list of covariates and other strata may be used in descriptive summaries and statistical analyses, some of which may also be used for subgroup analyses. Additional covariates and other strata of clinical interest may also be considered.

Category	Details
Strata	
Randomization Strata:
 
For the proportion of participants with plasma HIV-1 RNA ≥ 50 c/mL per FDA Snapshot algorithm at Week 48 (primary endpoint), a stratified analysis with Cochran-Mantel Haenszel weights will be used to adjust the primary treatment comparison for the randomization strata corresponding to prior exposure to CAB+RPV (0 weeks, 1-24 weeks, >24 weeks). A similar approach will be used to adjust the analysis of the proportion of participants with HIV-1 RNA <50 c/mL (per the FDA's Snapshot algorithm) at Week 48 (key secondary endpoint) and repeat analyses of these endpoints at Week 96.
 
See Section 7.1.5.1 for additional details on the statistical analysis methodology.

Other Subgroups / Covariates	See details in Section 5.4.2

5.4.2. Examination of Subgroups

The following is a list of subgroups that may be used in descriptive summaries and statistical analyses. Additional subgroups of clinical interest may also be considered.

- If the percentage of subjects is small within a particular subgroup, then the subgroup categories may be combined prior to un-blinding the trial.
- If the category cannot be refined further, then descriptive rather than statistical comparisons may be performed for the particular subgroup.
- For subgroup analysis, per European Medicines Agency Guideline on the investigation of subgroups in confirmatory clinical trials ([EMA, 2014](#)), factors defining a subgroup population may be put in three categories:

EMA Subgroup Category 1: Factors with strong reason to expect a heterogeneous response to treatment. In this case separate trials should usually be planned. There are no factors falling into this category in this study.

EMA Subgroup Category 2: Factors with at least some biological plausibility or external evidence such that a heterogeneous response might be hypothesized. In this study, stratified randomization strata, key demographic factors, Baseline CD4, CDC stage will be fall into this category. For these factors, subgroup analyses will be performed but likely underpowered so that a formal proof of efficacy will not be available individually

in all subgroups. If consistent findings across multiple comparisons were observed then these analyses would still be suggestive of a generalizable finding from the overall population.

EMA Subgroup Guideline Category 3: Factor with good argumentation why homogeneity of response to treatment is plausible. The impact of factors falling into this category will be explored.

- Additional covariates of clinical interest may also be considered.

Category	Covariates and / or Subgroups
EMA Subgroup Category 2:	
Randomization Strata	
 • Prior exposure to CAB+RPV (0 weeks, 1-24 weeks, >24 weeks) 
For analysis purposes, randomization strata will be rederived using eCRF data, even if this differs from the strata captured in RAMOS NG.
 
All statistical analyses will adjust for the above randomization strata, unless stated otherwise. Treatment-by-Strata interactions will be assessed as specified in the analysis sections.

Demographic and Baseline Characteristic Subgroups	
 • Age: 
 ○ < 35, 35 - < 50, ≥ 50 
For the statistical modelling, '< 35' and '35 - < 50' will be consolidated i.e. the following age group will be used:
 
 ○ < 50, ≥ 50 
For the summary of demographic characteristics, the following age groups will also be presented:
 
 ○ ≤ 18, 19 - 64, ≥ 65 (FDAAA requirement) ○ 18 - 64, 65 - 84, ≥ 85 (EMA requirement) • Race: 
 ○ White, Non-White ○ Black/African American, Non-Black/African American 
For the statistical modelling, only White vs Non-White is considered.
 • Sex at birth: 
 ○ Female ○ Male • Country (not used for statistical modelling) 
 ○ Argentina ○ Australia ○ Canada ○ France ○ Germany ○ Italy ○ Korea, Republic of ○ Mexico ○ Russian Federation

Category	Covariates and / or Subgroups
	
 ○ South Africa ○ Spain ○ Sweden ○ United States ● Baseline CD4+ cell count (cells/mm³): 
 ○ <350 ○ 350 - < 500 ○ ≥ 500 ● Baseline HIV-1 RNA (c/mL): 
 ○ <50 ○ ≥ 50 ● Derived Baseline Centers for Disease Control and Prevention (CDC) category: 
 ○ Stage I ○ Stage II ○ Stage III ● Prior Exposure to CAB+RPV: 
 ○ 0 weeks ○ ≥ 1 weeks 
This subgroup will be used in efficacy analysis, in addition to the rederived randomization strata (prior exposure to CAB+RPV: 0, 1-24, and >24 weeks). It will also be used in health outcomes analysis. In other types of analysis, only the rederived randomization strata will be used.
 ● Baseline BMI (kg/m²) 
 ○ <30 ○ ≥30 ● Baseline Third Agent Class: 
 ○ None (for subjects with prior exposure to CAB+RPV in ATLAS, i.e. subjects transitioned from ATLAS) ○ NNRTI ○ INI ○ PI

EMA Subgroup Category 3:
 
Additional subgroup/covariates for PK/PD efficacy analysis
	
PK/PD efficacy analysis will be performed for participants without prior exposure to CAB + RPV.
 
 ● Week 8 CAB/RPV Trough PK concentration (i.e. pre-dose PK concentration at nominal visit of Week 8) 
The above covariate will be dichotomized into two subgroup factors as follows:
 
 ○ ≤ first Quartile vs > first quartile, ○ ≤ Median vs > Median 
The concentration will also be treated as continuous variable in logistic regression modelling analysis (i.e. the concentration data will be log₂ transformed in this analysis so that, for assessing the effect,

Category	Covariates and / or Subgroups
	
one unit increase of the point estimate of log₂ PK concentration is equivalent to 'doubling the concentration' in the original value).
 
 Length of First CAB/RPV Injection Needle (<2, ≥2 inches)
Additional subgroup/covariates for PK/PD safety analysis	
Last CAB/RPV trough PK concentration
 
For the plot of Maximum Change from Baseline(CFB) in ALT/Total Bilirubin versus Last Trough CAB/RPV PK Concentrations, Last CAB/RPV Trough PK Concentration is the most recent trough PK concentration prior or equal to the date of the lab assessment with maximum CFB during the maintenance phase.
 
For the Plot of Maximum Toxicity Grades of Most Frequently Reported Study Drug ISR adverse events (AEs) versus Last Trough CAB/RPV PK Concentrations, Last CAB/RPV Trough PK Concentration is the most recent trough PK concentration prior or equal to the earliest onset date of the most frequently reported Study Drug ISR AE with maximum toxicity grade, during the maintenance phase. If a participant has no Study Drug ISR AE most commonly reported, then the last trough value during the maintenance phase will be used for the plot.

Additional subgroup for common drug-related study drug injection site reaction (ISR) with maximum toxicity grade	
For each preferred term of the common drug-related study drug ISR with maximum toxicity grade (pain, induration, nodules and any other study drug ISR with ≥5% subjects in either treatment arm) during the maintenance phase:
 
 Needle Length for Last CAB Injection prior to and including the onset date of the earliest corresponding drug-related CAB ISR with maximum toxicity grade during the maintenance phase: ≤1.5, >1.5 to <2, ≥2 inches Needle Length for Last RPV Injection prior to and including the onset date of the earliest corresponding drug-related RPV ISR with maximum toxicity grade during the Maintenance Phase: ≤1.5, >1.5 to <2, ≥2 inches 
Note: If there is no ISR of interest reported during maintenance phase for a subject, the needle length of last injection during maintenance phase will be used in the summary.

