8.1.1. Analyses for Injection Site Reaction Adverse Events from Study Drug Injection

Injection Site Reaction (ISR) adverse events of interest are those from study drug injections. For the summary of study drug ISR adverse events by visit and maximum severity (overall and by common ISRs): ISRs will be assigned based on onset date to the most recent planned IM injection visit prior or equal to the AE onset date.

Maximum grade at each visit will be derived as the maximum grade among ISRs assigned to the particular visit, with consideration for whether the summary applies to a particular preferred term (vs. across preferred terms), drug-related associated to CAB and/or RPV, or stratification by subgroup (such as needle length, refer to Section 5.4.2).

Drug-related ISRs (based on investigator discretion) from study drug injections will be attributed to the causal agent (CAB vs. RPV) when this can be determined specifically based on the side of injection administration and the side of the reported ISR (as collected in the eCRF). If we are unable to determine the causal agent in those cases where both drugs are given on one side and the ISR is reported non-specifically, then the attribution to a specific causal agent will remain unknown.

Common study drug ISR adverse events are defined by MedDRA preferred terms including injection site pain, injection site induration, injection site nodules and preferred terms of any other ISR with $\geq 5\%$ participants in either treatment arm, coming from study drug injections. The same set of common terms will be applied to 'overall' (CAB and/or RPV), CAB alone, RPV alone.

Study drug ISRs will be attributed to the needle length (≤ 1.5 , >1.5 to <2 , ≥ 2 inches) specifically based on the side of injection administration and the side of the reported ISR (as collected in the eCRF). If we are unable to determine the needle length for events where both drugs are given on one side and their needle lengths are different, then the attribution to a needle length will remain unknown.

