- t. Participants switching to CAB LA + RPV LA will take final dose of oral lead-in regimen in the clinic at the Week 4B visit and begin injections. If possible, injections should be spaced approximately 2 cm from one another and from the site of any previous injection and or any injection site reaction. Bring RPV LA to approximately room temperature prior to injecting. Time and location of injection (right or left) as well as needle length used will be collected in the eCRF. The first injection can be performed as soon as central lab results become available and safety parameters are reviewed.
- u. All Patient Report Questionnaires/Surveys will be administered via paper instrument at the beginning of the visit before any other assessments are conducted and prior to administration of the eC-CSSRS. Conduct questionnaires/surveys upon Withdrawal only if occurring at or prior to Week 48
- v. The HIVTSQc is to be administered to all participants transitioning from ATLAS and new participants transitioning from oral SOC. For participants transitioning from ATLAS, the version of the HIV-TSQc instrument to be administered will be based on the initial randomization arm at ATLAS Day 1
- w. For patients randomized to oral SOC at Day 1 in ATLAS or new patients on SOC, the reasons for willingness to switch ART will be assessed at Day 1. For patients randomized to CAB LA + RPV LA Q4W in ATLAS, the reasons for willingness to continue long-acting ART in ATLAS-2M will be assessed at Day 1.
- x. Preference Questionnaire will be administered to all participants
- y. Refer to Section 5.5 of the protocol for additional information on performing withdrawal assessments. HIV-1 RNA will be collected as Storage sample only if withdrawal assessments coincide with Week 52 or Week 100 (as per Section 5.5)
- z. Participants receiving one or more injections with CAB LA and/or RPV LA will be assessed with clinic visits at months 3, 6, 9 and 12 during the Long-Term Follow-Up Phase

Note: BP – Blood pressure, HR – Heart Rate, HDL – High Density Lipoprotein, LDL – Low Density Lipoprotein, PT Prothrombin Time, PTT Partial Thromboplastin Time, INR International normalized ratio

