No. in W48	No. in W96	No. in EOS	Population	IDSL / Example Shell	Title	Programming Notes	Deliverable
3.30	3.35	NA	Safety	201585/primary_02/T3.46	Summary of Study Drug Injection Site Reaction Adverse Events by Visit and Maximum Severity – Overall and Common (Maintenance Phase)	Change the second footnote to 'Note: Common ISR includes pain, induration, nodules and any other ISR with >=5% subjects in either treatment arm.' Footnote may be adjusted for clarifications.	W48, W96
3.31	3.36	NA	Safety	201585/primary_02/T3.47	Summary of Drug-related Study Drug Injection Site Reaction Adverse Events (Event-level Summary) - CAB (Maintenance Phase)		W48, W96
3.32	3.37	NA	Safety	201585/primary_02/T3.48	Summary of Drug-related Subject-level Characteristics of Study Drug Injection Site Reaction Adverse Events (Maintenance Phase) - Overall and Common (CAB)		W48, W96
3.33	3.38	NA	Safety	201585/primary_02/T3.49	Summary of Overall and Common Drug-related Study Drug Injection Site Reaction Adverse Events by Visit and Maximum Severity (Maintenance Phase) - CAB	Footnote may be adjusted for clarifications.	W48, W96
3.34	3.39	NA	Safety	201585/primary_02/T3.50	Summary of Maximum Drug-related Study Drug Injection Site Reaction Adverse Event Grade by Needle Length (Maintenance Phase) – Common (CAB)	Update the needle length in column header to be '<=1.5 inches', '>1.5 to <2 inches' and '>=2 inches' respectively. Change the first footnote to 'Note: Common ISR includes pain, induration, nodules and any other ISR with >=5% subjects in either treatment arm.'. Remove the second footnote.	W48, W96

Safety Tables							
No. in W48	No. in W96	No. in EOS	Population	IDSL / Example Shell	Title	Programming Notes	Deliverable
3.35	3.40	NA	Safety	201585/primary_02/T3.51	Summary of Drug-related Study Drug Injection Site Reaction Adverse Events (Event-level Summary) - RPV (Maintenance Phase)		W48, W96
3.36	3.41	NA	Safety	201585/primary_02/T3.52	Summary of Drug-related Subject-level Characteristics of Study Drug Injection Site Reaction Adverse Events (Maintenance Phase) - Overall and Common (RPV)		W48, W96
3.37	3.42	NA	Safety	201585/primary_02/T3.53	Summary of Overall and Common Drug-related Study Drug Injection Site Reaction Adverse Events by Visit and Maximum Severity (Maintenance Phase) - RPV	Footnote may be adjusted for clarifications.	W48, W96

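### The tables of ISR grade by needle length class participants at different times depending on outcome, so a net shift in needle mix can produce a needle-length difference where there is none

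*SAP*

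**What the plan says.** Section 5.4.2, in the row on common drug-related study drug ISRs, sets two rules for needle length.

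- Participants with the reaction are classed, for each preferred term, by the "Needle Length for Last CAB Injection prior to and including the onset date of the earliest corresponding drug-related CAB ISR with maximum toxicity grade". RPV has a parallel rule.
- For participants with no such reaction, "the needle length of last injection during maintenance phase will be used in the summary".

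The classes are ≤1.5, >1.5 to <2 and ≥2 inches. They are the columns of the displays titled "Summary of Maximum Drug-related Study Drug Injection Site Reaction Adverse Event Grade by Needle Length" in Section 15.14.5.4: Tables 3.34 (CAB) and 3.38 (RPV) at Week 48, and 3.39 and 3.43 at Week 96.

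Three other places bear on the point:

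- Section 8.1.1: "Study drug ISRs will be attributed to the needle length" by matching the side of the injection to the side of the reaction. This concerns events only.
- Footnote t of the schedule in Section 15.2.2: time and location of the injection, "as well as needle length used will be collected in the eCRF".
- Section 5.4.2, PK/PD efficacy covariates: "Length of First CAB/RPV Injection Needle", in two classes (<2, ≥2 inches), for an analysis restricted to participants without prior CAB+RPV exposure.

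**The concern.** In these tables the time at which a participant's needle is read depends on whether the participant had the outcome. Reactors contribute the needle used at some point during follow-up. Non-reactors contribute the needle used at the end. The numerator and the rest of the denominator can therefore sample different needle mixes.

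If the mix is stable, this does no harm. If it shifts on net, the columns gain or lose non-reactors for reasons unrelated to any effect of needle length, and the percentages separate. The separation could create a difference or hide a real one, and a reader could not tell this from the table. The two index times can also lie further apart at Week 96 than at Week 48, and a participant without a reaction can change column between the two reports.

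These four tables are the SAP's planned display of reaction grade against needle length, and their columns invite that comparison.

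**Working it through.** **Inputs.** The SAP states no figure on this point, so there is none to reproduce. From the SAP come the two classification rules (5.4.2) and the injection schedule (15.3.5). Without oral lead-in, Day 1 to Week 48 gives 48/4 + 1 = 13 injection visits in the Q4W arm and 48/8 + 1 = 7 in the Q8W arm. Everything else is assumed: two needle groups (short, long), one reaction per reactor, the same reaction risk *r* with either needle (true effect zero), and a short-needle share that starts at 85% and falls linearly to 80% or 70%.

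**Formula.** Let *a* be the share of a given needle among reactors at the time of reaction, and *b* its share at the last injection. The displayed incidence in that needle's column is

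*r·a* / (*r·a* + (1 − *r*)·*b*).

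This equals *r* only when *a* = *b*. There is no artefact if the mix has no net shift, or if every reaction follows the last injection.

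**Even spread, *r* = 50%, short share 85% to 80%.** With reactions equally likely at each injection, *a* for short needles is (0.85 + 0.80)/2 = 0.825.

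- Short: 0.4125/(0.4125 + 0.400) = 50.8%.
- Long: 0.0875/(0.0875 + 0.100) = 46.7%.
- False gap: 4.1 points.

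With a constant risk per injection among those still reaction-free, slightly more first reactions fall early. The gap is then 4.6 points (13 injections) or 4.7 points (7 injections).

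**All reactions at the starting mix, same inputs.** Now *a* = 0.85.

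- Short: 0.425/(0.425 + 0.400) = 51.5%.
- Long: 0.075/(0.075 + 0.100) = 42.9%.
- False gap: 8.7 points before rounding.

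**The four scenarios** (false gap, short minus long, in percentage points):

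| Incidence | Short share, first to last | Reactions spread evenly | All at starting mix |
|---|---|---|---|
| 50% | 85% to 80% | 4.1 to 4.7 | 8.7 |
| 50% | 85% to 70% | 9.7 to 11.1 | 21.5 |
| 20% | 85% to 80% | 2.5 to 2.7 | 5.2 |
| 20% | 85% to 70% | 5.9 to 6.1 | 12.2 |

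Front-loaded reactions fall between the two right-hand columns. The sign follows the shift: a move towards longer needles makes short needles look worse, and the reverse move makes long needles look worse.

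**Does a common index time remove it?** If everyone is classed at one outcome-independent time, *a* = *b* and each column shows *r*. A simulation of 400,000 participants with persistent needle switching (long share 20% to 30%, total risk 70%, 13 injections) agrees. The SAP rule gave 65.1% (long) against 71.8% (short). Classing everyone by first needle gave 70.2% against 70.0%, and by last needle 70.0% against 70.0%.

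**Does a per-injection table remove it?** With constant risk it does (0.0885 in both groups). With front-loaded risk and the same 20% to 30% shift, the unstratified per-injection rates were 0.115 (long) and 0.137 (short). That false gap arises because long needles were used more often later, when risk was lower. Stratifying by injection number removes it.

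**The case against.** The rule for reactors has a sound reason: it ties a reaction to the needle in use when it occurred, in line with the side-specific attribution in Section 8.1.1. Classing by first needle would give that up. This stands, and it bears on the choice of fix. It does not supply a matching rule for participants without a reaction.

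A reader might infer that any change in needle use produces a false effect. The documents do not support that. Individual switching with no net change in the mix gives no artefact, and neither do reactions confined to the last injection. Nor does the SAP show that the mix shifts at all. It records needle length but gives no needle-use data, and any reason for a shift, such as body habitus or earlier reactions, is conjecture.

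A reader might also take 8.7 or 21.5 points as the expected size. Those figures place every reaction at the starting mix, whereas the rule indexes on the earliest maximum-grade event, which can fall at any injection. With even spread they roughly halve.

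The table layouts follow shells that are not reproduced in the SAP, so the exact percentage basis cannot be confirmed. The note in Section 5.4.2 does place non-reactors in the summary by their last needle, so the mismatch is in the stated rule whatever the layout.

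Finally, these are descriptive tables with no planned test, in a group of factors that the SAP says it will only explore. Tables 3.2 and 3.3 also summarise needle length separately, but they do not link it to reactions and so do not repair the classification.

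**Conclusion.** The mismatch is real and nothing else in the SAP corrects it. Its effect is conditional: it needs a net shift in needle mix during the Maintenance Phase and at least some reactions before the last injection. Under the assumed scenarios with no true effect, the false gap runs from about 2.5 points (20% incidence, 5-point shift, even spread) to 21.5 points (50% incidence, 15-point shift, all reactions at the starting mix). Even spread at 50% incidence gives about 4 to 5 or 10 to 11 points. None of these rates comes from the SAP.

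The consequence is limited to the reading of four descriptive safety tables. It would go too far to infer that these tables are known to be biased in this trial, or that any efficacy conclusion is in doubt. The primary and key secondary comparisons do not use needle length. This is a minor improvement, worth making because it is cheap.

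**What to change.** Preferred: tabulate per injection. For CAB and RPV separately, and in the existing classes (≤1.5, >1.5 to <2, ≥2 inches), show the number of injections given and the share followed by a related ISR of each grade. Stratify by injection number or visit, because reaction risk may fall over time and an unstratified version can show its own false gap. This keeps each reaction with the needle in use and gives it a matching denominator.

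Alternative: class every participant, with or without a reaction, by the needle at the first CAB and first RPV injection in ATLAS-2M, using the same three classes. The first-needle covariate in the PK/PD efficacy analysis is a precedent but not a drop-in replacement. It has two classes and serves only participants without prior exposure, so the variable must be newly derived for all participants. The downside is that a later reaction may be counted under a needle that did not deliver that injection.

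Cost: a wording change in Section 5.4.2 and a revised derivation and layout for Tables 3.34 and 3.38 (Week 48) and 3.39 and 3.43 (Week 96). No new data are needed, because needle length is already recorded in the eCRF.

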5.5. Multiple Comparisons and Multiplicity

5.5.1. Primary Comparison of Interest

The primary analysis will be based on the ITT-E population. The primary comparison will be made at a one-sided 2.5% level of significance. Treatment with Q8W will be declared non-inferior to Q4W if the upper end of a two-sided 95% confidence interval for the difference between the two groups (Q8W – Q4W) in the proportion of participants with HIV-1 RNA ≥50 c/mL at Week 48 (defined by the US FDA snapshot algorithm) lies below 4%.

The primary comparison of interest is the comparison between Q8W (CAB LA + RPV LA Q8W) and Q4W (CAB LA + RPV LA Q4W) for the primary endpoint in the ITT-E population. This analysis will be adjusted for by the re-derived randomization strata based on eCRF data.

